4.3 Operational Term Definition

a) Air Leak

- For the purpose of this study, air leak is defined as the degree of the air that was noticed by the patients to be leak out via the interface (full face mask / nasal mask / nasal pillow) that was used during the CPAP trial for both types of CPAP machine.

b) Comfort

- For the purpose of this study, Comfort is defined as the ability of the patients to be able to fall asleep satisfactorily without interruptions while on the CPAP machine, and waking up in the morning feeling more refresh and energetic.

c) Compactness & Portability

- For the purpose of this study, Compactness & Portability is defined as the degree of assembling and operating the CPAP machine without any difficulties as well as the mobility of the machine in users' perspective.

d) Maintenance & Configuration

- For the purpose of this study, Maintenance & Configuration is defined as the feasibility to maintain the optimum state of the CPAP machine to serve its function accordingly. This includes cleaning the parts of the CPAP machine,

maintaining the humidifier and changing the filters.

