3.1.2 Secondary

1. To evaluate the efficacy between two CPAP machine (conventional Airsense 10and AirMini CPAP) in terms of AHI reduction.
2. To compare the average 95th centile pressure required using conventional Airsense 10and AirMini CPAP
3. To determine the correlation between the satisfaction score and reduction of AHI using Airsense 10and AirMini CPAP machine.
4. To compare the difference between conventional Airsense 10and AirMini CPAP in terms of:
 - a) Air leak
 - b) Comfort
 - c) Compactness & portability
 - d) Maintenance & configuration

Hypothesis

- 1) Patient's overall satisfaction is better using AirMini CPAP compared to AirSense CPAP machine.
- 2) There is no difference in terms of AHI reduction and average 95th centile pressure required between AirMini CPAP compared to AirSense CPAP machine.

- 3) There will be positive correlation between overall satisfaction and AHI reduction for AirMini CPAP compared to AirSense CPAP machine.
- 4) There is improvement in air leak, comfort, compactness and maintenance in AirMini CPAP machine compared to AirSense CPAP.

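### The compactness and portability item is defined by ease of set-up and mobility, not size, so its VAS cannot by itself support hypothesis 4's conclusion on compactness; separately, configuration in objective 4d has no defined content

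*Protocol*

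**What the plan says.** Objective 4 in protocol section 3.1.2 compares the two machines on four domains: (a) air leak, (b) comfort, (c) compactness and portability, and (d) maintenance and configuration. Hypothesis 4 in the same section uses shorter terms: "There is improvement in air leak, comfort, compactness and maintenance in AirMini CPAP machine compared to AirSense CPAP". Portability and configuration are not named there.

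The section headed Study Protocol and Data Acquisition lists a 100 mm VAS for overall satisfaction and for each of the four domains, with (c) and (d) under their paired labels.

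Section 4.3, Operational Term Definition, gives the content of each domain:

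- Item (c): "Compactness & Portability is defined as the degree of assembling and operating the CPAP machine without any difficulties", continuing "as well as the mobility of the machine in" the user's perspective.
- Item (d): "Maintenance & Configuration is defined as the feasibility to maintain the optimum state of the CPAP machine to serve its function accordingly". The examples follow: "This includes cleaning the parts of the CPAP machine", then "maintaining the humidifier and changing the filters".

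**The concern.** The definition of item (c) has two components. One is how easily the machine is put together and run, which is set-up and use. The other is mobility, which is portability. Compactness, the word on which hypothesis 4 concludes, has no component of its own. The literature review describes the AirMini as the newer, smaller and portable option, so smallness is one of the features by which the protocol itself distinguishes the devices, and it is absent from the definition.

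If subjects rate according to the definition, one mark on one line carries both set-up and mobility. A difference favouring the AirMini could then be reported as better compactness when it arose from easier assembly. A real difference in size could also fail to show. No later analysis can separate the parts, because only the combined mark is recorded. That makes it a matter for the protocol and not one that an analysis plan could repair.

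Item (d) has a smaller fault. Its label promises configuration, but the content given is upkeep. The nearest thing to configuration, assembling and operating the machine, is placed under (c).

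**Working it through.** No arithmetic applies: the point depends on no sample size, standard deviation or effect size. The check is to set label, definition and conclusion side by side.

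| Domain | Label in objective 4 and VAS list | Content in section 4.3 | Term in hypothesis 4 | Match? |
|---|---|---|---|---|
| (c) | Compactness and portability | Ease of assembly and operation; mobility | Compactness | Portability is covered by mobility; compactness is not covered; set-up is extra |
| (d) | Maintenance and configuration | Keeping the machine in good working state: cleaning, humidifier, filters | Maintenance | Maintenance is covered; configuration is not, but hypothesis 4 does not name it |

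**Item (c).** Suppose a subject follows the definition and gives set-up a weight w and mobility a weight 1 − w. The recorded difference between machines is then

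D = w × (difference in set-up) + (1 − w) × (difference in mobility).

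There is no separate term for size. Size enters only so far as it makes the machine easier to move. D can therefore differ from zero when the machines are equal in mobility, provided they differ in set-up. It can also be near zero when they differ in size. The weights are unknown and may vary between subjects. The protocol gives no expected difference or standard deviation for any domain, so D cannot be given a value, and its direction cannot be predicted.

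**Item (d).** The governing clause concerns keeping the machine in its best state, and the three listed tasks are all upkeep. Against hypothesis 4, which concludes on maintenance, the definition fits. Against objective 4d and the VAS label, which add configuration, it leaves half of the pair without content.

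**Count.** Of the four domain comparisons, one (c) is partly misaligned with hypothesis 4, and one (d) is misaligned with objective 4d and its own label only. Overall satisfaction is a separate VAS and does not draw on either definition.

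**The case against.** Four points can be made for the plan as written.

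1. Item (c) is a paired label, and mobility directly serves the portability half. This stands: it would be wrong to read the domain as defined by assembly and operation alone. It does not supply a measure of compactness, which is the half that hypothesis 4 names.

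2. The list in item (d) is introduced as non-exhaustive, and the general clause about serving its function might be stretched to cover settings. This stands in part. The clause is still about maintaining a state, and no set-up or configuration task is named anywhere in it.

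3. The questionnaire's wording is not in the text available for review. Subjects may see the section 4.3 definitions, the bare labels, or something else. This stands and limits the claim: the mixing of judgements is a consequence of the definition if it is used, not something shown to happen. But section 4.3 fixes the meaning of each term for this study, so the definition still governs how the result is to be interpreted.

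4. The definitions are declared to be for this study only, and where to file ease of assembly is partly a matter of preference. This is fair. It would settle the matter if the conclusion were worded in the same terms, but hypothesis 4 is not.

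A reader might go further and infer that two of the four VAS comparisons fail to measure what hypothesis 4 concludes. The document does not support that. Hypothesis 4 says maintenance, and definition (d) measures maintenance.

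**Conclusion.** The point holds as a minor one about secondary outcomes. Item (c) omits size and weight and includes ease of set-up and use, so a difference on it does not by itself support a statement about compactness. Item (d) leaves the configuration half of objective 4d undefined, with no consequence for hypothesis 4. The primary comparison of overall satisfaction is unaffected.

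The conclusion assumes that the section 4.3 definitions govern either how subjects rate or how the results are reported. A reader might also suppose that the AirMini is small but awkward to assemble, so that opposing judgements cancel on the line. Nothing in the protocol says that it is harder to assemble, and nothing ranks this domain as the one where the machines should differ most. No size or direction of bias should be claimed.

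**What to change.** In section 4.3:

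- Define (c) as the size and weight of the machine and the ease of carrying or moving it.
- Move the ease of assembling and operating the machine to (d), as its configuration content, next to cleaning, humidifier and filters.

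Then use the same paired terms, compactness and portability, and maintenance and configuration, in objective 4, hypothesis 4, the VAS items and any questionnaire text that repeats the definitions. Changing hypothesis 4 is a necessary part of this. If set-up moves into (d) while the hypothesis still says only maintenance, (d) would become broader than its conclusion, a mismatch that does not exist now.

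The cost is a wording change, with no extra data, visits or subjects. One drawback remains: (d) would still be a composite, covering set-up and upkeep on one line.

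The stated study period opens in September 2024, so ratings may already exist; the document does not say. If they were collected under the present definitions, do not change the wording midway. Instead, relabel item (c) and its conclusion as ease of set-up and use together with mobility, and draw no conclusion on compactness from it.

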4.4 Sample Size

This is a cross-sectional prospective study; hence the sample size calculation will be based on Machin et al. (2018) - *Machin, D., Campbell, M. J., Tan, S. B., & Tan, S. H. (2018). Sample Sizes for Clinical, Laboratory and Epidemiology Studies. doi:10.1002/9781118874905*

[figure not shown]
Table 16.2 Flat rule-of-thumb for the total sample size of a two equal-group comparative External-Pilot trial (partly based on Whitehead, Julious, Cooper and Campbell, 2015, Table 4).

Reference	N_{Pilot}
Birkett and Day (1994)	20
Julious (2005)	24
Kieser and Wassmer (1996)	20 to 40
Sim and Lewis (2011)	≥ 55
Browne (1995)	60*
Teare, Dimairo, Shephard, et al (2014)	≥ 70

*Actually recommended 30 for a single-arm study

The sample size decided for this study was 40 subjects. Considering and taking into account of about 10% dropout / missing data, hence the total sample size that will be recruited for this study are 50 subjects.

Data Collection Pathway

CHAPTER 5

RESEARCH ETHICS

Approval from the Research and Ethics Committee of Universiti Kebangsaan Malaysia Medical Centre (UKMMC) was done. All the collected information will be strictly confidential and only accessible by the research team members. All patients will be kept anonymous and coded into the data collection sheet.

Participants will only be recruited in this study once informed consent given, and will be allowed to withdraw from the study at any point. The research will be conducted according to the standard of good clinical practice and the rights and safety of the participants are guaranteed throughout the study.

GANTT CHART

Progression/Timeline	January 2023-March 2023	March 2023-July 2023	July 2023-August 2023	September 2023-September 2025	September 2025-November 2026
Literature review and proposal write up					
Proposal submission and correction					
Presentation to ethics committee and approval					
Patient recruitment and conduction of study					
Statistical analysis and preparation of result					
Manuscript writing and submission					

REFERENCES

References

- 1) American academy of sleep clinical practice guideline (<https://aasm.org/resources/factsheets/sleepapnea.pdf>)
- 2) National health and morbidity survey (https://iptk.moh.gov.my/images_Booklet_NHMS_2019)
- 3) (<http://codeblue.galencentre.org/2023>)
- 4) Malayisa e-cpg management of OSA (<https://www.moh.gov.my>)

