4.1 Type of Study

This is a prospective cross over trial study of group of patients with moderate to severe OSA based on the severity of the AHI.

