4.2 Study Protocol and Data Acquisition

This is a cross over trial that includes patients with medium to high risk of OSA according to STOPBANG score. Once these group of patients are selected, consent will be taken from them to go through a scheduled sleep study. Diagnosis is established after AHI score is concluded from the polysomnographic study. Those who are diagnosed with moderate to high AHI score will be recruited in this study. All subjects will be given a CPAP trial using both AirSense and AirMini model for 7 days each device. Upon recruitment, the subject will be randomised using 1:1 block randomisation either to receive Airsense CPAP machine or Airmini CPAP machine.

Those subjects that use AirSense CPAP machine first for 7 days will be given a set

of Questionnaire at the end of 7th day of the trial. Subsequently, they will be switch to use AirMini CPAP machine for another 7 days and the same set Questionnaire will be given on the 7th day of the trial. The type of the interface used will be based on subject's preferences, i.e., full face mask / nasal mask / nasal pillow, during the initial 1 – 2 days of CPAP trial. The same interface as per subject's preferences will be used throughout the CPAP trials for both AirSense as well as Airmini CPAP machine.

The Questionnaire given comprises of a 100mm Visual Analogue Score (VAS) for: 1) Overall satisfaction, 2) Air Leak, 3) Comfort, 4) Compactness & Portability, 5) Maintenance & Configuration. The data collected will be analyzed using SPSS Version 27.

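### Section 4.4 bases 40 subjects on a cross-sectional label and an external-pilot rule of thumb, although the trial is a randomised crossover with a comparative primary objective; its 10% loss step also does not lead from 40 to 50

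*Protocol*

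**What the plan says.** Section 4.4 labels the design and draws its method from that label: "This is a cross-sectional prospective study; hence the sample size calculation will be based on" a cited sample size textbook. The table reproduced from that book is captioned "Flat rule-of-thumb for the total sample size of a two equal-group comparative External-Pilot trial". Its rows run from 20 to at least 70, and one row reads 20 to 40. The section then states: "The sample size decided for this study was 40 subjects". It allows for "about 10% dropout / missing data, hence the total sample size that will be recruited for this study are 50 subjects".

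The design is described differently elsewhere. Section 4.1 says: "This is a prospective cross over trial study of group of patients with moderate to severe OSA". The section on study protocol and data acquisition (the second one numbered 4.2) says: "All subjects will be given a CPAP trial using both AirSense and AirMini model for 7 days each device". It adds that "the subject will be randomised using 1:1 block randomisation either to receive Airsense CPAP machine or Airmini CPAP machine"; a switch to the other device follows.

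Section 3.1.1 makes the comparison of overall satisfaction on a 100 mm VAS between the two devices the primary objective. The first hypothesis in section 3.1.2 is directional, in favour of AirMini.

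**The concern.** The word *hence* in section 4.4 makes the design label the reason for choosing the source, so the label does real work in the argument. A cross-sectional study has no two periods and no within-patient contrast. This trial has both. The table then answers another question: how many subjects an external pilot with two separate groups should have. Such a rule says nothing about the difference that a paired comparison can detect, or how precisely it will estimate that difference.

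At stake is how the primary result will be read. If the VAS comparison is not significant, the visible text offers no pre-stated detectable difference or interval width to set it against. Separately, a loss rate that does not connect 40 with 50 leaves the reader unsure which of the three figures was meant.

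**Working it through.** **1. Design label.** Set side by side, section 4.4 says cross-sectional, while sections 4.1 and 4.2 describe a crossover with both devices per subject, 7 days each, and 1:1 block randomisation of the first device. These cannot all be right. The detailed procedures agree with section 4.1, so the label in 4.4 is the error.

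**2. Loss step.** Inputs from section 4.4: 40 evaluable, about 10% loss, 50 recruited.

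- Dividing by the retained fraction: 40 / (1 − 0.10) = 44.4, so 45. With equal sequences the number must be even, so 46.
- Multiplying instead: 40 × 1.10 = 44.
- Neither gives 50. Loss implied by 50: 1 − 40/50 = 20%.
- Pairs expected if 50 are recruited and 10% are lost: 50 × 0.90 = 45.

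**3. The figure of 40.** It cannot be re-derived, because the visible text gives no alpha, sidedness, power, VAS difference, SD or interval width. It coincides with the upper end of one row of the pilot table, and the table as a whole does not single it out.

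**4. What the paired comparison would deliver.** Assumption: two-sided 5% (none is stated). Let δ be the mean difference divided by the SD of the within-patient differences. The detectable δ at 80% power solves P(T > t) = 0.80, where T is noncentral t with n − 1 degrees of freedom and noncentrality δ√n, and t is the 97.5% point of the central t with n − 1 degrees of freedom. The 95% CI half-width in SD units is t/√n.

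| Complete pairs | Arises from | Detectable, 80% power | Detectable, 90% power | CI half-width |
|---|---|---|---|---|
| 40 | 50 less 20% | 0.454 SD | 0.526 SD | 0.320 SD |
| 45 | 50 less 10% | 0.427 SD | 0.494 SD | 0.300 SD |

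Fitting a period effect (n − 2 degrees of freedom) changes these by at most 0.001 SD. The normal approximation, (1.960 + 0.842)/√n, gives 0.443 and 0.418 SD at 80% power, close to the table.

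**5. Conversion to mm, for illustration.** The protocol gives no VAS SD. If the SD of the differences were between 15 and 35 mm (assumed), the difference detectable at 80% power would be:

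- 40 pairs: 0.454 × 15 = 6.8 mm to 0.454 × 35 = 15.9 mm
- 45 pairs: 0.427 × 15 = 6.4 mm to 0.427 × 35 = 14.9 mm

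For an assumed true difference of 10 mm, 40 pairs have 98% power if the SD is 15 mm, 87% at 20 mm, 69% at 25 mm and 54% at 30 mm. The documents do not say where in this range the trial lies.

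**The case against.** The strongest objection is that the view is incomplete. A figure in section 4.4, placed between the citation and the table, is not shown, and it could hold further sample size material. This stands as a limit: the statement that power and precision are missing covers the visible text only. It does not touch the design label or the loss arithmetic, both of which rest on legible text.

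Second, no harm to the trial is shown. That is correct. A reader might infer that 40 subjects, or 50 recruited, is too few. The documents do not support this, because adequacy depends on an SD of differences that they do not give, and on the assumed values power ranges from ample to poor. The result can still be read from its confidence interval.

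Third, the loss step might be rescued by reading 10% dropout and a further 10% missing data: 40 / (0.9 × 0.9) = 49.4, so 50. The protocol does not say this, and a single combined 10% is the natural reading. A reader might also infer that the slip leaves the trial short. It does the opposite: 50 recruited at 10% loss leaves 45, five more than the target.

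Finally, 40 exceeds the number in the table's footnote, "Actually recommended 30 for a single-arm study". That footnote belongs to the same set of pilot rules, so it supplies no power or precision either.

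**Conclusion.** The point holds as a fault in the stated basis for the sample size, and it should be fixed. The design label contradicts sections 4.1 and 4.2. The only visible support for 40 is a rule for a different kind of study. On the natural reading, the stated 10% should be 20%, or the target should be 45 pairs; the discrepancy is conservative. The label and loss findings are firm. The absence of a power or precision statement is established for the visible text only.

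None of this shows that the trial is underpowered. In SD units, 50 recruited gives 80% power for 0.43 SD at 10% loss and 0.45 SD at 20% loss, assuming a two-sided 5% level and a paired analysis. Whether that is good enough depends on a VAS difference and an SD that the sponsor has to supply.

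**What to change.** In section 4.4:

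- Replace the cross-sectional label with *randomised two-period, two-sequence crossover*.
- Keep 50 recruited and restate the loss so that the figures agree: 40 complete pairs are retained with up to 20% loss, or 45 pairs are expected at 10% loss.
- Replace the pilot table as the basis with what the paired VAS comparison delivers at an alpha and sidedness that the sponsor states. If the sponsor chooses two-sided 5%, the text could read: *With 40 complete pairs the trial has 80% power for a mean difference of 0.45 SD of the within-patient differences (95% CI half-width 0.32 SD); with 45 pairs, 0.43 SD (0.30 SD).* Add a sourced SD of differences and a target VAS difference, so that these convert to mm and can be judged. Without them the sentence describes the sample size but does not justify it.

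The alternative is to declare the study a pilot with estimation aims and reword the first hypothesis to match. A pilot rule would then be an appropriate kind of basis, but the label and the loss step would still need correcting.

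If the figure not shown already contains a paired calculation, it should be brought into the text in place of the table.

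The cost is one reworded section and one sourced VAS assumption, with no change in enrolment, design or procedures. The drawback is that a stated detectable difference may look less favourable than an unstated one.
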